The objectives of this study are to clarify: what are the most salient social-ecological risk and resilience factors that should serve as targets for interventions and who are the survivors most at risk to be recruited for future interventions, how survivors want to receive educational interventions, and which educational interventions are most effective. Using a cross-sectional cohort study of 18-25 year old childhood cancer survivors and/or their parents, this study will determine predictors of transition readiness (Aim 1) and predictors of adherence to adult survivor-focused healthcare (Aim 2), as well as evaluate the quality (Aim 3) and efficacy (Aim 4) of electronic educational interventions for AYA survivors. The specific aims are to:

Aim 1: Evaluate social-ecological factors among AYA childhood cancer survivors participating in pediatric survivor care to determine factors associated with decreased transition readiness (i.e., risk factors) and increased transition readiness (i.e., resilience factors), as well as characterize patterns of co-occurring risk factors associated with transition readiness.

Aim 2: Evaluate social-ecological factors among AYA childhood cancer survivors following transfer to identify factors associated non-adherence (i.e., risk factors) and adherence (i.e., resilience factors) to adult survivor care, as well as characterize patterns of co-occurring risk factors associated with non-adherence to adult survivor care.

Aim 3: Develop and assess quality of electronic multimedia materials to educate AYA survivors about lifelong survivor care through qualitative interviews with AYAs.

Aim 4: Evaluate the impact of electronic educational materials on AYA survivors' knowledge about late effects, perceived benefits, self-efficacy, and intentions to engage in lifelong survivor care.

III. Study Design

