- *A2 Hypothesis 4:* When individual risk factors for non-adherence are included in principal component analyses (PCA), 2 or more components will emerge indicating subgroups at risk for poor transition outcomes.

Aim 3 Hypothesis:

- *A3 Hypothesis:* Stakeholder input and review of electronic media developed in this study using qualitative methods will increase acceptability and value to AYA survivors of childhood cancer

Aim 4 Hypotheses:

- *A4 Hypothesis 1:* Exposure to multimedia educational materials will significantly increase AYA survivors' knowledge about late effects and surveillance.
- *A4 Hypothesis 2:* Exposure to multimedia educational materials will significantly increase AYA survivors' perceived benefits of, self-efficacy to, and intentions to engage in survivor care across the lifespan.

A. Outcomes

For Aim 1, our metrics of “transition readiness” will be determined by patient- and parent-reported scores from the Readiness for Transition Questionnaire (RTQ-Overall). The RTQ-Overall assesses perceived preparedness to transfer both healthcare responsibility (from parent to teen) and services (from pediatric to adult care), with higher scores indicating increased transition readiness. For Aim 2, we will operationalize “adherence to adult survivor-focused healthcare” as the attendance of at least one healthcare visit with an adult provider focused on survivorship within 18 months following transfer from pediatric care. This operationalization of adherence was chosen based on recommendation by COG that survivors of childhood cancer should be evaluated annually and has been previously utilized to classify survivor clinic attendance. For participants who report attending an adult survivor care appointment, we will obtain a medical record release to verify date and attendance at an appointment with the adult survivor care provider. For Aim 3, we will elicit stakeholder feedback on the content, clarity, style, and interest-level of the electronic educational materials. For Aim 4, AYA health beliefs, knowledge

about survivor care and late-effects, patient activation, and self-efficacy and intentions to engage in lifelong survivor care will be evaluated using patient reported outcome (PRO) measures. In addition, a 15-item multiple choice quiz will be utilized to assess participants' knowledge of the content covered in the electronic educational materials.

B. Setting & Participants

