The clinical research aspects of this project will occur through Children's Healthcare of Atlanta's Aflac Cancer Survivor Program (CSP). Eligible participants will be patients of the Aflac Cancer Survivor Program and identified for recruitment using Aflac CSP clinical databases. Participants' CHOA electronic medical records will also be reviewed. The staff from the Aflac Cancer Center's Clinical Research Office has extensive experience in coordinating and managing clinical research projects with childhood cancer survivors. The Aflac CSP was established in 2001 and currently follows over 850 pediatric cancer survivors each year. This program consists of a multidisciplinary team (oncology, endocrinology, and pediatric psychology) who see patients for annual longterm follow-up survivor care beginning when the survivor is two years off therapy. Per CHOA policy, the Aflac CSP must transition patients to adult providers prior to age 22; however, patients are provided with the option to transition between the ages of 19 and 21 years.

For this study, we will be recruiting all eligible young adult survivor patients and/or one of their parents/caregivers. Participant inclusion criteria are as follows, patients must be 18-25 years of age, diagnosed with cancer at \leq 18 years of age, \geq 2 years since the last cancer treatment, and seen at least once in the Aflac CSP in the past 2 years (Aims 1, 3, & 4) or transitioned out of the Aflac CSP to adult survivor care since 2013 (Aims 2, 3, & 4). Although our goal is to enroll patient-parent dyads for Aims 1 & 2, patients and/or parents will be recruited individually and either may choose to participate or not to participate. Patient ineligibility will not impact parent eligibility and vice versa. Patients and/or parents will be excluded from participation in the study if the participant is non-English speaking. Young adult survivors who are cognitively impaired and unable to complete the questionnaires will be excluded. Any eligible subjects for Aims 3 & 4 will be excluded if they do not consent to the recording of their interviews.

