Following the completion of the AYA testing and interviewing, the electronic educational materials will be revised again using the quantitative and qualitative data collected as a guide to inform the revisions prior to dissemination.

D. Measures

Aims 1 & 2: Table 2 outlines the pre-existing factors and modifiable variables that we will assess and instruments we will use to measure these variables. After patients and parents have affirmed their willingness to participate via the electronic consent, they will be asked to complete a battery of self-report measures. The questionnaires will also be administered electronically using the REDCap platform. The surveys will take about 20-35 minutes to complete. Copies of the survey batteries from REDCap for Aims 1 & 2 are attached with this protocol. The following are links to the REDCap Consent and Survey:
<https://redcap.choa.org/redcap/surveys/?s=KNRMDF7WYX> (Aim 1)
<https://redcap.choa.org/redcap/surveys/?s=TPJY93F7TJ> (Aim 2)

Table 2. Methods and Measures (Aims 1 & 2)

Constructs	Method/Instrument
Patient Factors	

Demographics: Gender; Ethnicity; Age; Education; Employment	Demographics Questionnaire
Medical status & risk: Diagnosis; Treatment history & intensity; Late-effects risks, Global Health	Medical record review Intensity of Treatment Rating Scale (ITR-3) PROMIS v.1.1 – Global Health
Neurocognition: Executive Functioning; Perceived Cognitive Competence	Neurocognitive Questionnaire (CCSS-NCQ-R) Health Competence Beliefs Inventory (HCBI)
Developmental Maturity: AYA Autonomy; AYA Self-Efficacy	Health Competence Beliefs Inventory (HCBI) PROMIS SF v1.0 – Self-Efficacy Manage Emotions 4a PROMIS SF v1.0 – Self-Efficacy Manage Soc Inter 8a
Health Knowledge & Beliefs: Health Perceptions; Perceived Benefit of Survivor care; Perceived Vulnerability to Late-effects	Health Competence Beliefs Inventory (HCBI) Benefits Scale for Survivor Screening Absolute Perceived Vulnerability Survivor Knowledge Questionnaire (SKQ)
Psychosocial functioning: Anxiety, Depression, Social Isolation, Anger, & Post-Traumatic Stress Symptoms, Self-Esteem, Social functioning	PROMIS v1.0 Anxiety 8a & Depression 8a PROMIS v1.1 Anger 5a PROMIS v.2.0 – Social Isolation Impact of Events Scale-Revised (IES-R) Posttraumatic Growth Inventory (PTGI) Rosenberg Self-Esteem Scale PROMIS Pediatric Peer Relationships

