No biological specimens will be collected as part of this research. Participants' electronic medical records will be reviewed to abstract treatment data. Confidentiality within this study will be rigidly maintained. Computer files will use study identification numbers only and are password protected. Only necessary personnel will have access to any of these files. Based on existing best practices for security and privacy in health information technology, we will identify the technologies and features to be employed to ensure privacy and security of personal information. This will address identity and access management, secure storage, secure messaging, encryption, and other security technologies and approaches.

VI. Statistical Analysis Plan

Aims 1 & 2: In 2015, the Aflac Cancer Survivor Program (Aflac CSP) saw over 200 AYA survivors aged 18-22 years (Aim 1). Additionally, the Aflac CSP has transitioned approximately N=165 survivor patients since 2013 (Aim 2). Based on our previous research with survivor patients > 18 years of age, we estimate that less than 2% of AYAs will be non-English speakers. During the year-long study period, we anticipate that there will be at least N=200 AYA patients who are eligible for participation in Aim 1 and at least N=160 AYA patients who are eligible for participation in Aim 2. Previous studies with our AYA population have yielded initial recruitment rates and retention rates above 80%. Of the eligible AYA patients, we estimate that 75% [Aim 1: N=220 patient-parent dyads (440 participants), Aim 2: N=120 patient-parent dyads (240 participants), Aim 3: N= 20 patients, Aim 4: N=58] will participate in each aim of the study. In our univariate analysis, these sample sizes provide us with at least 80% or greater power to detect correlations of magnitude ≥ 0.25 and odds ratios of at least 2.5, depending on the prevalence of the risk factor, assuming that approximately 20-30% of patients meet our definition of successful transition. Power analyses were conducted using PASS v. 11 (Kaysville, UT) using a two-sided test for a single correlation and a two sample Z-test for proportions. Given these anticipated numbers, we can assess at most 15 possible predictors for aim 1 and 12 predictors for aim 2 to ensure that we have at least 10 observations per predictor in our principal component analysis.

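### Aim 2 analyses an 18-month outcome as yes/no, but sets no minimum time since transfer and no rule for survivors surveyed before 18 months have passed

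*Combined protocol and SAP*

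**What the plan says.** - **Outcome.** III. Study Design, A. Outcomes, defines Aim 2 adherence as "attendance of at least one healthcare visit with an adult provider focused on survivorship within 18 months following transfer from pediatric care". For participants who report a visit, a record release is sought so that its date and attendance can be verified.
- **Eligibility.** III.B, Setting & Participants, admits survivors aged 18-25 who "transitioned out of the Aflac CSP to adult survivor care since 2013 (Aims 2, 3, & 4"). This bounds the transfer date on one side only.
- **Age at transfer.** The same section says that "the Aflac CSP must transition patients to adult providers prior to age 22" and that "patients are provided with the option to transition between the ages of 19 and 21 years".
- **Data collection.** II. Goals/Aims Overview describes the design: "Using a cross-sectional cohort study of 18-25 year old childhood cancer survivors and/or their parents". III.C and III.D describe one online battery for Aim 2 and no re-contact after it is completed.
- **Predictors.** Table 2 lists, as demographic patient factors, "Gender; Ethnicity; Age; Education; Employment".
- **Analysis.** VI. Statistical Analysis Plan treats successful transition as a binary outcome, tested by chi-square and/or logistic regression. Predictors that pass a 0.1 screen enter a principal component analysis. No censoring method, re-check or time-since-transfer rule is given.

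**The concern.** The outcome needs 18 months of observation after transfer, and nothing ensures that each participant has had them. A survivor surveyed at 8 months who has not yet attended is neither adherent nor non-adherent under the definition. Record verification does not help. It is triggered by a reported visit, so it can correct a false or late 'yes' but cannot settle a 'no' given too early.

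The plan leaves three treatments of these open windows available to the analyst:

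- Score open-window survivors without a visit as 'no'. The adherence rate is then too low.
- Drop only those survivors and keep open-window attenders. The rate is then too high.
- Drop every open-window survivor, whatever the visit status. This avoids the bias but costs sample size.

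Under the first two, the error depends on time since transfer, so any predictor that varies with it can appear related to adherence when it is not. Age varies with it by construction, because transfer falls in a narrow age band. Identifying factors associated with adherence is the purpose of Aim 2, so a false signal of this kind could carry through the screen into the components.

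**Working it through.** **Inputs from the documents.** Window 18 months = 1.5 years. Planned Aim 2 sample 120 (0.75 × 160 = 120, which reproduces). Success rate 20-30%, odds ratio 2.5, two-sample Z-test, 10 observations per predictor. Transfer at 19 to under 22; age under 26 at survey.

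**Assumptions, because the documents give no figure.** Transfers even over Y = 3 to 7 years before the survey; transfer age even over 19-22; visits of eventual attenders uniform over the 18 months; two-sided 0.05; half of the sample exposed.

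**Step 1: share of open windows.** With transfer age a, only survivors with time since transfer below 26 − a remain eligible, and 26 − a runs evenly from 4 to 7. The mean eligible span is m = mean of min(Y, 26 − a), and the open share is f = 1.5/m. For Y of 3 or 4, m = Y. For Y = 5, m = (1/3)(4.5) + (2/3)(5) = 4.83. For Y = 6, m = (1/3)(4.5 + 5.5 + 6) = 5.33. For Y = 7, m = 5.5.

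**Step 2: apparent adherence rate.** Let q be the true rate and s the share of open-window eventual attenders already seen (0.5 for uniform visits).

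- Scored 'no': A = q[1 − f(1 − s)].
- Only open-window non-attenders dropped: A / [1 − f + fqs].
- Completed windows: 120(1 − f).

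| Y | m | f | scored 'no', q = 30% | dropped, q = 30% | completed windows of 120 |
|---|---|---|---|---|---|
| 3 | 3.00 | 0.500 | 22.5% | 39.1% | 60 |
| 4 | 4.00 | 0.375 | 24.4% | 35.8% | 75 |
| 5 | 4.83 | 0.310 | 25.3% | 34.4% | 83 |
| 6 | 5.33 | 0.281 | 25.8% | 33.9% | 86 |
| 7 | 5.50 | 0.273 | 25.9% | 33.7% | 87 |

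Visit timing matters. If visits fall in months 0-12 (s = 0.67), the ranges are 25.0-27.3% and 41.7-34.9%. If they fall in months 6-18 (s = 0.33), they are 20.0-24.5% and 36.4-32.5%.

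**Step 3: a predictor unrelated to time since transfer.** An odds ratio of 2.5 with an overall rate of 20% means group rates of 12.9% and 27.1%; with 30%, 20.6% and 39.4%. Scoring 'no' multiplies both by 1 − f/2, which is 0.75 at Y = 3 and 0.864 at Y = 7. The apparent odds ratio is 2.37-2.43 (20%) or 2.29-2.38 (30%).

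Power by the pooled two-sample Z-test:

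| Overall rate | N = 120, no misclassification | scored 'no', Y = 3 to 7 | completed windows only, N = 60 to 87 |
|---|---|---|---|
| 20% | 49% | 37-42% | 28-38% |
| 30% | 61% | 45-53% | 35-48% |

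Restriction therefore costs 22-11 points (20%) or 26-13 points (30%); scoring 'no' costs 12-7 or 16-9. The N = 120 figures are below the plan's stated 80% for an odds ratio of 2.5. That is a separate matter, and nothing here depends on it.

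**Step 4: a predictor that tracks time since transfer.** Split the sample at the median age, with no true age effect. At Y = 3 the older half has 75% completed windows and the younger half 25%. The shares of eventual attenders already seen are 0.917 and 0.583. At q = 30%:

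- Scored 'no': 27.5% v 17.5%, odds ratio (0.275/0.725)/(0.175/0.825) = 1.79.
- Dropped: 0.275/0.80 = 34.4% v 0.175/0.35 = 50%, odds ratio 0.52.

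Simulation over Y = 3-7 and q = 20-30% gives about 1.5-1.8 scored 'no', 0.5-0.6 dropped and 1.0 with completed windows only. At N = 120, age passes the 0.1 screen about 20-37% of the time if scored 'no' and 24-34% if dropped, instead of 10%.

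**The case against.** **Hypothesised predictors are not shown to be affected.** Age is in no Aim 2 hypothesis, Table 2 lists more constructs than the 12-predictor limit, and no section says that age will be chosen. The documents do not link health beliefs, maturity, responsibility or parental involvement to time since transfer. This stands. A reader might infer that the Aim 2 hypothesis tests are seriously biased; the documents do not support that. The age figures also rest on a median split that the plan does not use, so they illustrate the mechanism only.

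**Restriction can cost more than the flaw.** For predictors unrelated to time since transfer, limiting the analysis to completed windows loses more power than scoring 'no' (step 3). This stands, and it is why restriction should not be the first remedy.

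**The sample-size counts might seem to show that everyone will be scored.** The plan says that "the Aflac CSP has transitioned approximately N=165 survivor patients since 2013 (Aim 2") and that "we estimate that less than 2% of AYAs will be non-English speakers". A reader might note that this leaves about 162 of 165, close to the 160 expected to be eligible, and infer that no recent transfers were set aside. The inference fails. The 165 is a count to date, while 160 is a forecast for a year in which new transfers enter and others pass age 25. Survivors too cognitively impaired to complete the questionnaires are also excluded. The counts do not show which rule is intended.

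**Records are checked, and the survey may collect dates.** Verification improves the 'yes' answers but leaves early 'no' answers unresolved. The Aim 2 battery is attached to the protocol but not available here, so it may ask for transfer and visit dates. Even so, no eligibility or analysis rule in the text uses them.

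**Conclusion.** The gap is real and should be fixed. Eligibility, data collection and analysis as written admit survivors whose Aim 2 outcome cannot be determined, and two of the treatments left open bias the adherence rate in opposite directions. Confidence is high for the missing rule and for the mechanism, but not for the size, because survey dates, the spread of transfers and visit timing are not given.

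Under the stated assumptions, about 50-27% of windows are open and a true 30% appears as about 22.5-25.9% (scored 'no') or 39.1-33.7% (only open-window non-attenders dropped). False associations are a risk for predictors that track time since transfer. For other predictors the distortion is small: an odds ratio of 2.5 appears as about 2.3-2.4 when open windows are scored 'no'.

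**What to change.** 1. **Main analysis.** In III.A (Outcomes) and VI (Statistical Analysis Plan), define the Aim 2 outcome as time from transfer to first adult survivor visit, censored at the earlier of survey and 18 months. Estimate the 18-month rate by Kaplan-Meier and associations by Cox regression. This keeps all participants and removes the time-since-transfer bias, provided that recent and earlier transfers have similar visit patterns given the predictors.
2. **Sensitivity analysis, or main analysis if visit dates are unavailable.** Score the binary outcome only for survivors surveyed at least 18 months after transfer, whatever their visit status. Do not keep open-window attenders while dropping open-window non-attenders.
3. **If the restricted binary analysis is the main one,** restate evaluable N, power and number of predictors in VI. Under the assumptions above, about 60-87 of 120 remain, so 6-8 predictors at 10 observations each instead of 12.

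**Cost.** The time-to-event analysis needs the transfer date, which program records should supply, and the visit date, which the plan already seeks to verify; where no release is returned it would have to be self-reported. The restriction costs about 11-26 points of power for an odds ratio of 2.5 (20-30% read as the overall rate, half exposed). Neither analysis changes the fact that predictors are measured at the survey, after the visit for attenders, so results should be reported as associations only.

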DISSEMINATION: Share AYA educational material via implementation toolkits (R01 CA218389-01) & Post material on www.cancersurvivorlink.org educational platform & share with registrants via email

For Aim 3, eligible stakeholders will be recruited (N=20 AYA survivors) via phone or in clinic by a member of the Aflac Cancer Survivor Research team, and survivors interested in participating will be verbally consented via WebEx. Example questions are outlined in Table 3. These stakeholder reviews will be used to inform revisions to the infographics and videos, which will be made prior to engaging in Aim 4.

For Aim 3 and 4, all interviews will be recorded for transcription/qualitative data analysis.

The consent and interview processes in Aim 3 will be completed sequentially during the subject's webex interview; therefore, this consent discussion will be recorded. All Aim 3 subjects must verbally consent to this recording prior to the recorded consent process. Once the subject has consented to recording, the recording will begin. The study staff will follow Aim 3 telephone scripts for the entire consenting process. Telephone scripts for Aim 3 are included in this protocol.

Once the interview recording begins, study staff will ask if the subject has provided recording consent (for documentation purposes). Next, all subjects will have to confirm their identity (for security and data validity purposes) by providing their name and date of birth. The information provided by the subject must match the information gathered in Epic for the main study consenting to begin. Subjects will then go over the main study and verbally consent for their participation in it.

For Aim 4, we will recruit a total of N=58 AYA survivors to evaluate our revised electronic educational materials (eligibility requirements described above). Recruitment procedures will be the same as in Aim 3 except that in Aim 4, subjects will review and complete consent online as in Aims 1 & 2. The initial page of the REDCap survey will contain a brief online consent outlining the purpose of the study, its voluntary nature, time commitment,

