incentive information, release of PHI, and contact information of PI and Emory IRB should a participant have questions. To record participants' consent to participate, we will have them click a radio button labeled "Yes, I agree to take part" or "No, I do not want to take part". We will also have participants insert the current date. Participants who select "Yes, I agree to take part" will be routed to the study survey battery following their typed signature. Participants who select "No, I do not want to take part" will exit the REDCap system and route to a screen that thanks them for their consideration. Copies of the online consent from REDCap are attached with this protocol.

After consenting to Aim 4, participants will be asked to complete an online pre-test survey via REDCap. The pre-test will be the first step in a survey queue from REDCap. After subjects complete the pretest, the queue will allow them to review the materials that were created for Aim 4 within the REDCap platform. If the survey queue is started but not finished, study staff may contact the consented subjects via phone call, text or email in order to remind them to finish. Study staff will confirm receipt and review of material and schedule a post-test survey to be completed in REDCap two weeks after material is reviewed (the date when initial survey queue is completed).

These pre- and post-tests will be designed to assess AYA health beliefs, knowledge about survivor care and lateeffects, and self-efficacy and intentions to engage in lifelong survivor care. We have selected scales to assess participants' health beliefs and intentions (Table 3, and will generate a 15-item multiple-choice quiz to assess participants' knowledge of the content covered in the electronic educational materials). The pre- and post-test should take approximately 20-25 minutes each to complete. Up to five reminders will be sent to ensure survey completion.

At the time of initial consent for Aim 4, subjects will have the option to participate in telephone exit interviews via Zoom (N=25), lasting 30 minutes. All Aim 4 exit interviews will be recorded for transcription purposes and conducted 2-3 weeks following completion of the post-test. Example questions are outlined in Table 3.

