Aims 3 & 4: Qualitative data analysis should be conducted until data “saturation”, or the point at which no new information is likely to be garnered from additional interviews/focus groups. Given that previous research has indicated that over 85% of analytic themes are identified within the first 12 interviews, we are confident that we will reach saturation of new information with N=20 stakeholder interviews with AYA survivors in Aim 3, as well as N=25 AYA post-test interviews in Aim 4. In order to analyze our qualitative data, separate codebooks for analyzing data will be developed at each stage of the formative evaluation using thematic analyses based on guide questions and evaluation attributes. Following development of the codebooks, each response will be coded by two independent raters. Open coding methods will be used to analytically evaluate the data and comparisons will be made for data similarities and differences. A qualitative analysis software package, NVivo, will be used to assist in the identification of patterns and relationships between concepts (i.e., acceptability, appropriateness). Frequencies of all codes will be tabulated and used to inform the revision of the electronic educational materials by types. Differences in the frequency of codes will be examined among subgroups of AYA small group participants (i.e., age, years post diagnosis, gender) using Chi-square and ANOVA analyses. Our team and the Winship Cancer Institute’s Intervention Development, Dissemination and Implementation (IDDI) core has vast experience with qualitative and mixed methods analyses.

In Aim 4, paired t-tests or Wilcoxon signed-rank tests will be used to compare AYA HBM constructs and knowledge about survivor care and late-effects before and after reviewing the electronic educational material. Given 58 AYA survivors, we will have greater than 80% power to detect an average of a 1.5 point increase (or an effect size of 0.40) in AYA average knowledge score after reviewing the electronic educational materials.

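### Aim 4 gives no post-test date to survivors who do not finish the materials queue, and its power statement leaves no room for lost pairs

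*Combined protocol and SAP*

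**What the plan says.** Section III.C (Procedures & Recruitment, Aims 3 & 4) makes the pre-test the first step of a REDCap queue that then opens the materials. Staff confirm that the materials were received and reviewed, and "schedule a post-test survey to be completed in REDCap two weeks after material is reviewed (the date when initial survey queue is completed"). No other starting point for the post-test is given. For an incomplete queue the provision is: "If the survey queue is started but not finished, study staff may contact the consented subjects via phone call, text or email". The same section adds "Up to five reminders will be sent to ensure survey completion".

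On numbers, section III.C says "For Aim 4, we will recruit a total of N=58 AYA survivors to evaluate our revised electronic educational materials", and Table 1 sets the same 58 against the pre-test and post-test step. Section VI (Statistical Analysis Plan, Aims 3 & 4) says "Given 58 AYA survivors, we will have greater than 80% power to detect an average of a 1.5 point increase", equates that gain with an effect size of 0.40, and names paired t-tests or the signed-rank alternative. Its last paragraph gives an SD of 4.0 points for the paired change and a significance level of 0.05. It names no analysis set, missing-data rule or dropout allowance for Aim 4. The only retention figure is in the Aims 1 & 2 paragraph of section VI: "Previous studies with our AYA population have yielded initial recruitment rates and retention rates above 80" per cent.

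**The concern.** Whether a survivor is measured a second time depends on whether that survivor finished the exposure. Someone who takes the pre-test, opens the materials and stops has a baseline score but no scheduled follow-up score, and a paired test cannot use that person. These survivors are the ones best placed to show whether the materials hold attention. They also fall out of the exit interviews, which are timed from completion of the post-test, although those interviews ask what was unclear or unappealing. Aim 4 results feed the second revision and then dissemination, so the gap falls where the study most needs the information. An outcome that was not collected cannot be recovered at analysis.

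The second strand is precision. The number recruited and the number of complete pairs behind the power statement are the same 58, so any loss comes straight off the stated power.

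**Working it through.** **Inputs**
- Recruited: 58 (section III.C).
- Gain to detect: 1.5 points, also given as effect size 0.40 (section VI).
- SD of the paired change: 4.0; alpha 0.05 (section VI, last paragraph).
- Sidedness: not stated for Aim 4. Two-sided is assumed, as section VI states for the correlation test in Aims 1 & 2.
- Loss between pre-test and post-test: not stated for Aim 4. A range of 0 to 20% is assumed. The upper end treats the cited retention of above 80% as exactly 80%.

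**Formula.** Paired t-test power from the noncentral t distribution, with n − 1 degrees of freedom and noncentrality d × √n, where d = mean gain / SD of change.

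**Step 1: the effect size.** 1.5 / 4.0 = 0.375, not 0.40. An effect size of 0.40 would correspond to 0.40 × 4.0 = 1.6 points.

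**Step 2: the plan's own figure.** With n = 58 and d = 0.375, noncentrality is 0.375 × √58 = 2.86 and power is 0.802. This agrees with the stated power of more than 80%. It is also the smallest n that reaches 80% on these inputs.

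**Step 3: fewer pairs** (58 × retained share, rounded down)

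| Complete pairs | Loss from 58 | Power, d = 0.375 | Power, d = 0.40 |
|---|---|---|---|
| 58 | none | 0.802 | 0.850 |
| 57 | one pair | 0.795 | 0.843 |
| 55 | 5% | 0.780 | 0.830 |
| 52 | 10% | 0.756 | 0.808 |
| 49 | 15% | 0.730 | 0.783 |
| 46 | 20% | 0.702 | 0.756 |

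At 0.40, 52 is the smallest number that keeps 80%, so 58 − 52 = 6 pairs can be lost. At 0.375 none can.

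**Step 4: detectable gain.** With 46 pairs, 80% power needs d = 0.422, which is 0.422 × 4.0 = 1.69 points.

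**Step 5: sensitivity to sidedness.** With a one-sided 0.05 test, power at 58 pairs and d = 0.375 would be 0.880, and 46 pairs would still reach 80%. The table therefore depends on the two-sided assumption. That 58 is exactly the two-sided minimum at 0.375 suggests that this is how the number was chosen.

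**The case against.** The strongest reply concerns the question being asked. The Aim 4 hypotheses are about exposure to the materials, section III.D places the post-test after they have been viewed, and section VI compares scores before and after review. Measuring people who reviewed the materials answers that question. This stands. A reader might infer that an analysis of completers is wrong and that everyone who started should be the main result. The documents do not support that. Such an analysis would also mix people measured two weeks after review with people measured after partial review or none.

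Second, the loss is conditional. Up to five reminders, staff confirmation of review and gift cards for both surveys (section IV) all work against it, and if all 58 finish, all 58 pairs stand. The retention figure comes from earlier studies and is a lower bound, so 46 pairs is a floor and not a forecast. This also stands, but none of these measures gives a post-test date to someone who still does not finish.

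Third, queue completion is not full viewing. No measure of how much was viewed is described, so someone who clicks through could still be post-tested. It would go too far to say that only fully exposed survivors are measured.

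Finally, non-finishers who ignored reminders may also ignore a fallback post-test, and ordinary post-test non-response is not cured by a new date. The recovery may be modest.

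**Conclusion.** The concern holds as a gap in the plan. Survivors with unfinished queues have no route to a post-test, and the power statement has no allowance for loss. On the plan's point-scale inputs and a two-sided test, power runs from 0.802 with 58 pairs to 0.702 with 46. At the stated effect size of 0.40 it runs from 0.850 to 0.756 and stays above 80% down to 52 pairs. The shortfall is moderate and rests on an assumed loss of up to 20%.

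Two stronger readings are not supported. A reader might infer that the stated power is wrong; it reproduces for 58 complete pairs, and only the effect-size label is inconsistent with the other inputs. A reader might also infer that the reported gain is shown to be inflated. If finishers gained 1.5 points and non-finishers none, the mean over all starters would be 1.5 × 0.80 = 1.20 to 1.5 × 0.90 = 1.35 points with 80 to 90% finishing. But zero gain in every non-finisher is an extreme assumption, and the documents give neither their gain nor their number. Overstatement relative to all starters is plausible in direction; its size is unknown.

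**What to change.** 1. In section III.C, keep the current date for queue completers. Add that pre-test completers who have not finished the queue receive the post-test at a fixed time after the pre-test. Three weeks would match the spacing in Table 1 (1 week + 2 weeks). Record queue status from REDCap.
2. In section VI, keep the result in those who reviewed the materials as the answer to the exposure hypotheses. Report beside it the result in everyone with both a pre-test and a post-test, with the numbers who started, finished the queue and were post-tested.
3. In section VI, correct the effect size to 0.375, state that the test is two-sided if that is intended, and restate power for the complete pairs expected from 58 recruited: about 70 to 80% for 1.5 points with 46 to 58 pairs, or 80% for about 1.7 points with 46.

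The sample need not be enlarged. Protecting 58 pairs would take 58 / 0.90, 58 / 0.85 or 58 / 0.80, that is 65, 69 or 73 recruits at 10, 15 or 20% loss. For a formative evaluation, an accurate power statement is the proportionate change.

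Cost: a short wording change, one REDCap invitation rule, one extra table, a few more gift cards and a less favourable stated power.
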